5.1 Recruitment

We will employ several recruitment methods for this trial.

A. Stanford University Clinical Virology Laboratory

The primary method of recruitment is in partnership with laboratories performing SARS-CoV-2 testing. Patients with a positive SARS-CoV-2 test will be identified from the laboratory, and with receipt of a positive test, patients will be sent an email or letter inviting them to contact the study staff for screening and enrollment if interested.

The Clinical Virology Laboratory at Stanford University, which conducts the vast majority of Northern California's SARS-CoV-2 testing will be our first laboratory partner. Recruitment could be expanded to include additional laboratories nationwide.

B. Flyers/Social Media

We will also use flyers to advertise the study at COVID-19 testing locations and public spaces. Social media platforms will also be used such as Facebook, Twitter, and Instagram. We will also use social media to create an online ad campaign for the study. Please see the appendix for a template of the social media documents.

C. Study Website

We will create a study specific website designed to recruit participants and provide more information about the study. The website can be found here: <https://proctor.ucsf.edu/action-trial>. The link to the REDCap screening questionnaire can be found directly on the website. The website also contains contact information, frequently asked questions, and eligibility criteria.

Participants can contact study staff if they are interested by phone at [contact] or by emailing [contact].

D. Open Door Health, Rhode Island

Open Door Health in Providence, Rhode Island will also assist with recruitment activities for this project. Open Door Health is one of the first primary care centers in Rhode Island that is dedicated to serving LGBTQ+ Rhode Islanders. The facility serves a large Black, Hispanic/Latinx, and immigrant population. The coordinators at Open Door Health will help recruit participants by passing out flyers and providing COVID positive patients with the study email and phone number.

E. Every Door Direct Mail with USPS

Every Door Direct Mail, or EDDM, is targeted marketing with the US postal service. We will create a postcard advertising the study. We will then work with the US postal service to deliver the postcard to residences along mail routes in selected zip codes. The postcard will contain study info, the study website, and the study contact info. Interested participants can call or email us directly or visit the study website. See the appendix for an example of the postcard used.

F. WebMD

WebMD is an online platform for news and information regarding human health. WebMD publishes COVID-19 specific information which reaches approximately 14 million people per month. Advertising ACTION on WebMD's COVID content pages enables us to reach potential participants nationwide. We will place electronic ads as banners on their website. Interested participants can click 'learn more' and then they will be directed to the study screening form.

5.2 Enrollment

Interested participants will be remotely screened for eligibility prior to enrollment. Participants can be screened by phone or by an electronic REDCap form accessible from the study website. If eligible, study staff will call the participant and collect informed consent electronically via DocuSign. Upon determining eligibility and signing electronic informed consent documents, study staff will ask the participant to provide their mailing address. Study staff will then mail the participant their randomized treatment allocation, self swabbing materials, and email an electronic baseline questionnaire. No contact between study staff and participants in this trial will take place as to minimize risk of infection spread. At the end of the screening questionnaire, we will collect phone number and email information from the eligible participants. We will also require patients to provide proof of their positive test result by uploading documentation through REDCap.

The data analyst will inform the coordinator daily of the new eligible participants. Coordinators will then call participants to review the study and informed consent form.

5.2.1 Informed Consent

Consent scripts will be submitted and approved by the UCSF IRB committee in San Francisco, California prior to study implementation. The informed consent document will be sent electronically to eligible participants with the Experimental Subject's Bill of Rights. Children under the age of 18 will not be eligible. All participants will be informed about the possible risks

and benefits of treatment. If the participant wishes to withdraw themselves from the study, they may do so at any time.

The informed consent form will be sent electronically to the participant's email address via DocuSign while the coordinator is on the phone with the patient. The coordinator will review the form with the patient. If the patient wishes to participate, they will sign the form electronically. Electronic signed consent forms will be uploaded to the UCSF Box account for ACTION.

5.2.1.1 Informed Consent for Spanish Speaking Participants

We will utilize the UCSF IRB's "preferred method" of informed consent for Spanish speakers. A qualified translator will translate all study documents including the informed consent document, the study surveys, the patient instructions, and all study documents. Spanish speaking participants will be called over the telephone with a study staff member and a qualified medical interpreter. The communication plan is outlined below:

1. If a participant submits a screening form, the study staff will contact the medical interpreter to set up a time to call the participant. Once a time is established, the study staff will call or text the participant in Spanish to confirm the time.
2. If a Spanish speaking potential participant calls the study phone number, the study staff member will attempt to communicate that we will call back with the interpreter. A follow-up text will be sent in Spanish confirming a time the medical interpreter will call back to review the study and informed consent.
3. If a participant submits an English screening form, we will follow the steps from item #1 listed above and move this participant into the Spanish REDCAP project for ACTION. The English record ID for this participant will be deleted after transferring their information to the Spanish REDCAP project. This ensures that the participant will receive all study documents in Spanish throughout the study.

5.2.1.2 Informed Consent for Non-English and Non-Spanish Speakers

We will utilize the IRB's "short form method" to consent non-english and non-spanish speakers. The Experimental Subject's Bill of Rights form will be presented to the subject in their primary language. An interpreter will translate the UCSF IRB approved consent form to the subject. The consent discussion will occur with the study staff member, interpreter, and subject on the phone simultaneously. The subject will sign the Bill of Rights form and the interpreter obtaining consent will sign the English consent form.

5.2.1.3 Informed Consent for Computer Illiterate Participants

Some participants may be unable to navigate email and DocuSign to provide their electronic signature on the consent document. In this case, several steps will be taken in order to obtain informed consent from these participants.

1. The translator or coordinator will review the steps from the document “How to use DocuSign” over the phone with the participant. See appendix for this document.
2. If the participant is still unable to use email and/or DocuSign, we will ask if there is anyone in the subject’s household who could assist them with using the computer to open the ICF document. The participant will sign on their own.
3. If the subject is still unable to navigate the consent form, we will explain that we will mail them two paper copies of the consent form with FedEx Priority First Overnight mail. We will call the participant back when they have received the package and review the consent form with them while they have the paper copy in front of them. We will then ask them to sign one copy of the consent form and mail it back to us in a provided pre-paid FedEx envelope. The participant will place the package outside their front door and the UCSF coordinator will organize the FedEx pick up for them. The participant keeps the second copy of the ICF.

5.3 Baseline Assessment

Once a participant is determined eligible for the study and informed consent has been signed, they will be asked to complete an electronic baseline questionnaire via REDCap. Participants will be asked to provide information about their health and contact information in order to facilitate follow-up. Next of kin information will be collected in the event that the patient is unresponsive due to hospitalization or death. Please see the questionnaire in the appendix.

Participants unable or unwilling to electronically complete the questionnaires themselves may call the study coordinator who can fill out the survey on their behalf over the phone. Participants may also utilize a designated alternate, such as a family member, to fill out the electronic questionnaire on their behalf. The coordinator will make a note on the patient Masterfile if they filled out a questionnaire on the subject’s behalf.

A sub-set of participants in the swab sub-study will be asked to collect a nasal swab at baseline.

5.4 Treatment

Participants will receive a single oral dose of azithromycin (1.2 g) or placebo in the mail directly to their home. The treatment will come as an oral suspension. The patients will receive instructions for how to administer the treatment. Participants will be unaware if they have received azithromycin or placebo. Details on study medication are outlined in Chapter 7. Only eligible participants will be treated.

5.5 Day 3 Assessment

Three days after treatment, participants will be asked to complete a brief adverse event survey. They will also be asked to self-collect sample specimens, if they are willing to. The first will be a nasal swab. The second will be a saliva swab. The third swab will be a rectal swab. The swab

kits will be mailed to the patient directly. Patients will have detailed instructions outlining how to collect the swabs. The swab procedure is outlined in Chapter 6. After collecting the swabs, the patient will mail the specimens back to the UCSF Proctor Foundation for analysis. Directions for shipping the samples back to the Proctor Foundation will be provided. We will mail participants pre-assembled category B biological substance shipping materials and a pre-paid shipping slip. Participants will call FedEx directly to schedule a pick-up or they will contact the study coordinator to schedule the pick-up for them.

Participants may opt out of the swab collection if they wish to do so. During the initial screening questionnaire, we will ask if participants are willing to collect the swabs. Participants can still participate in the trial, opting to only receive the medication and not perform the swabs.

Some participants may be willing to participate in the swab sub-study (determined at consent). These patients will be asked to collect saliva, rectal, and nasal swabs at Day 3. They will only collect these swabs once, and they will not collect Day 3 swabs as part of the main study.

5.6 Day 7 Assessment

Participants will complete a questionnaire 7 days post baseline. The questionnaire will ask about the patient's health status and hospitalization status. The REDCap questionnaire will be sent electronically to the patient's email address.

A small subgroup of patients (100 per arm) will be asked to collect a rectal, saliva, and nasal swab at the Day 7 timepoint.

5.7 Day 14 Assessment

Participants will complete an electronic follow-up questionnaire at 14 days post treatment. This is our primary endpoint. We will contact the next of kin provided by the participant during enrollment for vital status and hospitalization information for participants who do not return their electronic questionnaire within 4 days of the due date.

A small subgroup of patients (100 per arm) will be asked to collect a rectal, saliva, and nasal swab at the Day 14 timepoint.

5.8 Day 21 Assessment

A final electronic REDCap survey will be sent to participants at day 21. This is the final study questionnaire. The questionnaire will be similar to the Day 14 survey. Information about the patient's health and hospitalization status will be collected.

5.9 Reminders

Participants will be sent reminders if the questionnaires are not completed. The first reminder will be sent via email 1 day after non-completion. A text reminder will be sent 2 days after non-completion. A study coordinator will call the participant if the questionnaire is not completed within 3 days. If the respondent fails to answer the 14-day timepoint questionnaire, the study coordinator will call the next-of-kin emergency contact if the questionnaire is not completed within 4 days of the due date.

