3.4.2 Secondary Outcomes

Secondary outcomes will include

- **Hospitalization:** Defined as any visit to the emergency room or other hospital setting that resulted in a stay of 24 hours or more.
- **Adverse events:** we will conduct an adverse event survey at Day 3 after treatment, including gastrointestinal side effects (nausea, vomiting, diarrhea, abdominal pain) and rash. We note that some COVID-19 patients report gastrointestinal symptoms, and this survey will provide data on whether azithromycin causes additional gastrointestinal effects beyond those symptoms.
- **Prevalence of positive swabs:** we will compare the prevalence of SARS-CoV-2 positive swabs at Day 3 after treatment in self-collected nasal, saliva, and rectal swabs in azithromycin compared to placebo-treated participants.
- **Viral load:** we will assess viral load by RT-PCR in self-collected nasal, saliva, and rectal swabs at Day 3 after treatment.
- **Mortality:** we will collect emergency contact/next of kin information during the baseline questionnaire. We will follow-up with the emergency contact if participants are lost to follow-up at the Day 14 questionnaire to assess mortality and hospitalization outcomes.
- **Genetic macrolide resistance determinants:** We will evaluate the prevalence of genetic macrolide resistance determinants *ermB*, *mefA/E*, and *mphA* by targeted PCR in rectal samples collected at Day 3 after treatment.
- **COVID-19 symptoms:** we will ask patients about COVID-19 symptomology during each online questionnaire, including cough, fever, myalgia, anosmia, shortness of breath (and related abilities such as ability to walk across a room or up a flight of stairs), fatigue, conjunctivitis, and orthostatic symptoms.

- **Number of emergency room visits:** during each online questionnaire we will survey patients about any emergency room visits (with stays <24 hours) that occurred since their last survey.
- **Number of household members with COVID-19 (confirmed or symptomatic):** during each online questionnaire we will ask participants how many of their household members have symptoms of COVID-19 or confirmed disease.
- **Death:** we will attempt to link deaths among participants to the National Death Index.

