#### Secondary Outcomes:

- **Hospitalization and/or death by 14 days** after the electronic enrollment assessment.
- **Hospitalization/death by 21 days:** we will extend follow-up beyond the primary endpoint to capture any hospitalizations or death that progress more slowly and are not detected by 14 days.
- **Adverse events:** we will conduct an adverse event survey at Day 3 after treatment, including gastrointestinal side effects (nausea, vomiting, diarrhea, abdominal pain) and rash. We note that some COVID-19 patients report gastrointestinal symptoms, and this survey will provide data on whether azithromycin causes additional gastrointestinal effects beyond those symptoms.
- **Prevalence of positive swabs:** we will compare the prevalence of SARS-CoV-2 positive swabs at Day 3 after treatment in self-collected nasal, saliva, and rectal swabs in azithromycin compared to placebo-treated participants.
- **Viral load:** we will assess viral load by RT-PCR in self-collected nasal, saliva, and rectal swabs at Day 3 after treatment.
- **Mortality:** we will collect emergency contact/next of kin information during the baseline questionnaire. We will follow-up with the emergency contact if participants are lost to follow-up at the Day 14 and Day 21 questionnaires to assess mortality and hospitalization outcomes.
- **Genetic macrolide resistance determinants:** We will evaluate the prevalence of genetic macrolide resistance determinants *ermB*, *mefA/E*, and *mphA* by targeted PCR in rectal samples collected at Day 3 after treatment.
- **COVID-19 symptoms at 21 days:** we will ask patients about COVID-19 symptomology during each online questionnaire, including cough, fever, myalgia, anosmia, shortness of breath (and related abilities such as ability to walk across a room or up a flight of stairs), fatigue, conjunctivitis, and orthostatic symptoms.
- **Number of emergency room visits:** during each online questionnaire we will survey patients about any emergency room visits (with stays <24 hours) that occurred since their last survey.
- **Number of household members with COVID-19 (confirmed or symptomatic):** during each online questionnaire we will ask participants how many of their household members have symptoms of COVID-19 or confirmed disease.

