### **Secondary Outcomes:**

- **Hospitalization/death by 21 days:** We will use a Kaplan-Meier approach to account for losses to follow-up. We will use Greenwood's formula to estimate the standard error of the log proportion in each arm will be used to determine the variance of the risk difference at 21 days.
- **Mortality by 21 days:** we will collect emergency contact/next of kin information during the baseline questionnaire. We will follow-up with the emergency contact if participants are lost to follow-up at the Day 14 and Day 21 questionnaires to assess mortality and hospitalization outcomes.
- **COVID-19 symptoms at 21 days:** we will ask patients about COVID-19 symptomology during each online questionnaire, including cough, fever, myalgia, anosmia, shortness of breath (and related abilities such as ability to walk across a room or up a flight of stairs), fatigue, conjunctivitis, and orthostatic symptoms.
- **COVID-19 (confirmed or symptomatic) among household members of enrolled patients:** during each online questionnaire we will ask participants how many of their household members have symptoms of COVID-19 or confirmed disease. This analysis will be conducted on an expanded dataset that includes an observation for each household member. To account for outcome correlation among individuals within households, we will estimate 95% confidence intervals for the risk difference and risk ratio with a clustered, non-parametric bootstrap that resamples households with replacement (10,000 iterations).

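### The protocol triggers next-of-kin contact only for a missed Day 14 form, while the SAP relies on it at Day 21 too, so late hospitalizations can be missed in the 21-day secondary analysis

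*Protocol*

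**What the plan says.** Three protocol sections describe the next-of-kin call, and each ties it to Day 14:

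- Section 5.9 (Reminders): "If the respondent fails to answer the 14-day timepoint questionnaire, the study coordinator will call the next-of-kin emergency contact", once the form is 4 days overdue.
- Section 5.7 (Day 14 Assessment) has the same call, "for participants who do not return their electronic questionnaire within 4 days of the due date".
- Section 3.4.2 (Secondary Outcomes) has it "if participants are lost to follow-up at the Day 14 questionnaire to assess mortality and hospitalization outcomes".

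Section 5.8 begins "A final electronic REDCap survey will be sent to participants at day 21" and contains no next-of-kin step.

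The SAP goes further. In both 6.1 and 6.2 the mortality entry reads: "We will follow-up with the emergency contact if participants are lost to follow-up at the Day 14 and Day 21 questionnaires". The stated purpose covers hospitalization as well as death.

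Hospitalization or death by 21 days is a SAP secondary outcome, included to pick up events that come too late for the 14-day assessment. For its analysis SAP 6.2 says: "We will use a Kaplan-Meier approach to account for losses to follow-up". The missing-data sensitivity analyses in SAP 6.3 are written for the 14-day endpoint only.

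Protocol 5.3 explains that next-of-kin details are held because a participant may fail to respond as a result of hospitalization or death.

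**The concern.** Coordinators take their instructions from the protocol. As written, it gives them no reason to ring a relative when the Day 21 form is missing, so the step the SAP counts on has no operational trigger.

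The gap falls in the window that the 21-day outcome was added to cover. Kaplan-Meier treats a censored person as having the same later risk as those still followed. Protocol 5.3 anticipates the opposite, since being in hospital can itself be the reason a form is missing. Where that happens, censoring removes events selectively and the 21-day risk is understated. Protocol Appendix 1 records that hospitalization proved much rarer than expected, so a handful of missed events is a noticeable share of the total.

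**Working it through.** **Text comparison (current text of both documents)**

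| Place | Next-of-kin contact after a missed form |
|---|---|
| Protocol 3.4.2 | Day 14 |
| Protocol 5.7 | Day 14, after 4 days |
| Protocol 5.8 | None stated for Day 21 |
| Protocol 5.9 | Day 14, after 4 days |
| SAP 6.1 | Day 14 and Day 21 |
| SAP 6.2 | Day 14 and Day 21 |

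**Who falls through.** A Day 14 non-responder is covered: the call comes at about Day 14 + 4 = 18 and may pick up some late events. The uncovered person answers at Day 14, is hospitalized on Days 15 to 21, and does not return the Day 21 form.

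**Size.** The plan states no rate for Day 21 non-response or for late hospitalization, so there is no figure to reproduce. Everything below is an assumption, except N = 455 and the 20% loss to follow-up, which SAP 3.3 uses for the 14-day outcome and which is borrowed here for Day 21. I also assume that everyone at risk answers at Day 14 and that Day 21 non-responders are censored at Day 14.

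Let r be the true risk in Days 15 to 21, m1 the Day 21 non-response among those hospitalized in that window, m0 the non-response among the others, and S14 the event-free proportion at Day 14. Then

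- observed late risk = r(1 − m1) / [r(1 − m1) + (1 − r)(1 − m0)]
- Kaplan-Meier 21-day risk = 1 − S14 × (1 − observed late risk)

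*Illustration 1: share of events missed and effect on the estimate.* Take a total 21-day risk of 3% to 5%, one third of events late, m1 = 50%, m0 = 20%.

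- Events: 455 × 0.03 = 13.7 to 455 × 0.05 = 22.8.
- Missed: × 1/3 × 1/2 gives 2.3 to 3.8 events, or 1/6 = 17% of all events.
- Effect on the estimate: Kaplan-Meier also removes the other non-responders from the risk set. The late risk is therefore multiplied by about 0.5/0.8 = 0.625, a 37.5% shortfall in the late third. Overall that is 0.375 × 1/3 = 12.5%. The exact formula at a 3% total gives 2.63% instead of 3.00%, which is 12.4% too low.

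*Illustration 2: range.* 14-day risk 3%, m0 = 20%, m1 = 50% to 80%.

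| True late risk r | True 21-day risk | Kaplan-Meier 21-day risk | Late events missed |
|---|---|---|---|
| 0.5% | 3.49% | 3.30% to 3.12% | 1.1 to 1.8 of 2.2 |
| 1% | 3.97% | 3.61% to 3.24% | 2.2 to 3.5 of 4.4 |
| 2% | 4.94% | 4.22% to 3.49% | 4.4 to 7.1 of 8.8 |

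With m1 = m0 = 20% the Kaplan-Meier risk equals the true risk in every row. With a 14-day risk of 10% the shortfall is similar, 0.2 to 1.3 percentage points.

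**Effect on the comparison.** If late risk and non-response are the same in both arms, the risk difference is the Day 14 difference times (1 − r). At r = 1% and m1 = 50% the observed late risk is 0.005/(0.005 + 0.792) = 0.63%, so the multiplier is 0.994 rather than 0.990, which is no material change. The difference shrinks when the arms truly differ in late hospitalization. If ascertainment differs by arm, it can move as well.

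**The case against.** The best case against the point is that the SAP plainly promises the Day 21 contact and no protocol sentence forbids it. That the call is made only at Day 14 is inferred from silence in 5.8. Protocol 5.3 holds the contact details for a purpose not limited to one visit, and Protocol 14.1 plans vital status at Day 21. Other routes also exist. Email, text and coordinator-call reminders apply to every questionnaire, a family member may complete the form, and deaths can be recovered from the National Death Index.

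Much of this stands. It rules out the stronger reading a reader might infer, that 21-day hospitalizations are lost as a matter of course. The documents support only that they can be.

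It does not close the gap. The reminders go to the participant, who may be in hospital. Completion by a relative is voluntary and not prompted by the study. The Death Index does not record hospitalizations. The hospitalization verification sub-study (Protocol 3.3) starts from participants already known to have been hospitalized, and the serious adverse event definition in Protocol 11.3 does not list hospitalization as a criterion, although some cases could qualify as important medical events.

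A second objection is scale. With 303 and 152 participants and about 4% risk, the standard error of the risk difference is √[0.04 × 0.96 × (1/303 + 1/152)] ≈ 1.9 percentage points. A 12% shrinkage of an assumed 2-point difference is 0.24 points, so this alone is unlikely to change a conclusion about efficacy. That stands too. The case for the change is an unbiased 21-day risk and consistent documents at small cost.

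**Conclusion.** The contradiction between Protocol 3.4.2, 5.7, 5.8 and 5.9 and SAP 6.1 and 6.2 is real and lies in current text. If the protocol text is followed, hospitalizations on Days 15 to 21 can be censored because of the event itself, and the 21-day Kaplan-Meier risk can be understated.

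The size depends on rates the documents do not give. Under Illustration 1, about 17% of events are missed and the risk is about 12% too low; the two figures measure different things and should not be interchanged. If non-response does not depend on hospitalization, there is no bias.

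Two further inferences are not supported. The treatment difference is not diluted in general, only if the arms differ in late hospitalization or in how it is ascertained. The primary outcome, symptom-free status at Day 14, is not touched. The point concerns hospitalization or death by 21 days and, much less, mortality, which has the Death Index behind it. It should be corrected, but it does not threaten the trial's main conclusion.

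**What to change.** Add to Protocol 3.4.2, 5.8 and 5.9 the rule already used at Day 14: call the next of kin if the Day 21 form is not returned within 4 days of its due date, to establish vital status and hospitalization. This matches the SAP. The call would fall at about Day 25, so check it against the 21-day study period in Protocol 3.7; the existing reminders already run to Day 24. Deleting the Day 21 contact from the SAP would also make the documents agree, but would leave the gap open.

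Extend the SAP 6.3 sensitivity analyses to the 21-day outcome, since calls will not reach everyone. The missing-not-at-random shift analysis matters most here, because weighting on baseline characteristics cannot correct for censoring caused by a later event.

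The cost is a short protocol amendment, calls by the existing coordinator using details already held, and a little more analysis. If the 20% planning loss applied at Day 21, that would be 0.20 × 455 = 91 calls over the whole trial.
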